Title:

3-year Evaluation of the Clinical Performances of a Self-adhesive Hybrid Resin Composite Compared to a Traditional Composite Resin Used for Direct Restorations of Non-carious Cervical Lesions (NCCLs): A Split-mouth Randomized Clinical Trial

Identifier: NCT05751382

Document date: 9-Feb-2024

3-year Evaluation of the Clinical Performances of a Self-adhesive Hybrid Resin Composite Compared to a Traditional Composite Resin Used for Direct Restorations of Non-carious Cervical Lesions (NCCLs): A Split-mouth Randomized Clinical Trial

Sponsor

Dentsply DeTrey GmbH
[name],
[name]
Germany

Principal Investigator

[name]
Clinica Odontoiatrica (DIBINEM)
[name]
[name]
Italy

Anticipated number of study sites: 1 study site.

Anticipated number of subjects: 50 (split-mouth design, i.e. Surefil one n=50, and Venus Pearl n=50).

Background and overall aim

Non carious cervical lesions (NCCL) are often restored due to dental sensitivity caused or for aesthetic reasons and in order to prevent further loss of mineralized tissue, with consequent pulp exposure. Numerous protocols of treatment have been proposed for V class cervical lesions. Treatment depends on the location and degree of dental materialized tissue loss, however, as soon as the lesion exposes the dentin, the restorative treatment may become necessary. Restorative therapy is often complicated by the absence of sufficient enamel tissue, dentin sclerosis and difficulty in isolation of the field. Furthermore, since the class V lesions tend to involve the anterior segments of the dental arches an incongruous restoration or pigmentations on the margins could affect the patients' smile. Current research is directed towards the development of new materials and the improvement of the adhesion between the restorative materials and the mineralized dental surface trying to respect as much as possible the healthy dental tissues, and to obtain an impeccable aesthetics. In fact, we know that an unsatisfactory aesthetics is the main cause of rebuilding a restoration in the anterior section, unlike the posterior sectors where the main motivation for reintervention is bacterial infiltration that causes secondary caries.

The aim of this study will be to demonstrate non-inferiority in terms of clinical performance and patient discomfort after direct restorative treatment of class V NCCL with Surefil one restorative material (Dentsply Sirona) in comparison with traditional paste composite "Venus Pearl" employed in combination with iBond universal adhesive (Kulzer Dental) during an observational period of 3 years.

Study objectives

Primary objective

The primary objective is assessment of restorative quality at 36 months follow-up using FDI and USPHS criteria.

Secondary objectives

The secondary objectives are to evaluate:

- Restorative quality at 6-, 12- and 24-months follow-up using FDI and USPHS criteria.
- Aesthetics at 6-, 12-, 24- and 36-months follow-up.
- Level of pain at 6-, 12-, 24- and 36-months follow-up.
- Time needed to perform the restoration.
- Safety

Study design

This is a split-mouth randomized clinical investigation conducted to evaluate clinical performances of a self-adhesive hybrid resin composite (investigational medical device Surefil) compared to a traditional composite resin, when used for direct restorations of non-carious lesions (NCCLs). The study consists of a 3-year long follow-up period.

Study population

All patients will be treated at the Department of Conservative Dentistry of the University of Bologna, Italy. Patients showing NCCL will be screened to assess if they are eligible for participation according to below criteria.

Inclusion criteria

For inclusion in the study subject must meet all of the following criteria:

1. Patients aging from 18 to 70
2. 40-60% women, 40-60% men
3. Patients who present at least 2 cervical lesions on canines and / or upper premolars on vital teeth
4. Patients who are not allergic or sensitive to the ingredients contained in the products
5. The test patient consents to the restorative treatment in line with the study's criteria (informed consent)
6. Sufficiently understanding of the language

Exclusion criteria

Any of the following is regarded as a criterion for exclusion from the study:

1. Extremely low level of oral hygiene
2. Teeth with previous restorations
3. Not possible adequate isolation of the operating area
4. Patients with serious systemic diseases
5. Devitalized teeth or with pulpitis in progress
6. Periodontal problems on the elements to be restored

Materials employed in the study

Adhesives: iBond Universal Adhesive (Kulzer, Germany).

Composites:

- Surefil one (Dentsply Sirona, Germany)
- Venus Pearl (Kulzer, Germany)

Indication

Surefil oneTM self-adhesive composite hybrid is a permanent bulk fill material for posterior restorations.

Data Analyses:

The differences between the two groups will be analyzed using a descriptive and inferential statistical analysis. The statistical analysis will be performed by the department of Biomedicinal and Neuro-Motor Sciences (DIBINEM) of the University of Bologna.

Study timetable

Anticipated study start:	Sep 2022
Anticipated completion:	Sep 2026

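### The aim is to demonstrate non-inferiority, but the plan sets no margin, no single defined endpoint and no decision rule, so it cannot yield a prespecified non-inferiority conclusion

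*Combined protocol and SAP*

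**What the plan says.** The last paragraph of Background and overall aim sets out to "demonstrate non-inferiority in terms of clinical performance and patient discomfort after direct restorative treatment of class V NCCL" with Surefil one, against Venus Pearl used with iBond, over 3 years.

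Under Primary objective: "The primary objective is assessment of restorative quality at 36 months follow-up using FDI and USPHS criteria". Under Secondary objectives, the same domain is assessed earlier ("Restorative quality at 6-, 12- and 24-months follow-up using FDI and USPHS criteria"), and the entry closest to discomfort is "Level of pain at 6-, 12-, 24- and 36-months follow-up".

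Study design describes a within-patient comparison ("This is a split-mouth randomized clinical investigation conducted to evaluate clinical performances of a self-adhesive hybrid resin composite"). The title page gives the number of subjects as "50 (split-mouth design, i.e. Surefil one n=50, and Venus Pearl n=50", without a calculation.

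Data Analyses has two sentences. One is "The differences between the two groups will be analyzed using a descriptive and inferential statistical analysis"; the other names the department that will do the work. The section shows no sign of redaction or a missing table, and no separate analysis plan is mentioned.

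**The concern.** A non-inferiority hypothesis is defined by its margin. Without one there is nothing to test, and a confidence interval, however well computed, gives no verdict.

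The primary objective fixes a domain, a time point and two instruments. It does not say which instrument decides, which item or score is compared, or what counts as success. Discomfort is part of the non-inferiority claim, yet pain appears only as a secondary objective at four visits.

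Two things are at stake:

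- The same 36-month data could be reported as non-inferior or not, depending on a margin chosen afterwards.
- With only an analysis of differences planned, a non-significant result may be taken for non-inferiority. At this sample size it is a common result even when the test material is materially worse.

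Restorative quality is also assessed at 6, 12 and 24 months. Nothing says that comparative results are seen before 36 months, but if they were, a margin set later could follow the data.

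**Working it through.** **1. Inputs.** The documents supply 50 pairs, one restoration per material per patient, and a 36-month primary time point. They supply no margin, alpha, sidedness, power, success rate or SD, within-patient correlation or attrition. All other inputs below are assumptions, and the results are illustrations only.

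**2. The plan's own figure.** N = 50 cannot be reproduced. For a binary outcome with equal true success rates p and within-patient correlation ρ, the normal approximation is

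n = 2p(1−p)(1−ρ)(z_α + z_β)² / margin².

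At one-sided 2.5% and 80% power, (1.960 + 0.842)² = 7.85.

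- p = 0.85, ρ = 0, margin 5 points: 0.255 × 7.85 / 0.0025 ≈ 801 pairs.
- p = 0.95, ρ = 0.5, margin 20 points: 0.0475 × 7.85 / 0.04 ≈ 9.3, so 10 pairs.

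The requirement runs from 10 to 801 pairs, so 50 implies no particular margin.

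**3. One data set, two verdicts.** Suppose 45/50 successes per side, with b = 4 pairs where only the test restoration succeeds and c = 4 where only the comparator does. The paired score (Tango) statistic for margin D is

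z = (b − c + nD) / √[n(2q + D − D²)],

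where q is the restricted estimate of the test-only probability. With these data q solves 100q² − kq − 4D(1−D) = 0, with k = 4(1−D) − 8D + 4(1−D) − 84D.

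- D = 0.10: k = −2.0, q = (−2 + √148)/200 = 0.0508, z = 5/√(50 × 0.1917) = 1.62, below 1.96. Not shown.
- D = 0.15: k = −7.0, q = (−7 + √253)/200 = 0.0445, z = 7.5/√(50 × 0.2166) = 2.28, above 1.96. Non-inferior.

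The 95% lower limit, where z = 1.96, is −12.5 points.

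**4. How far the margin drives the verdict.** This is exact enumeration of all discordant-pair tables for 50 pairs with the comparator at 90%. The both-succeed probability is p_t·p_c + φ√[p_t(1−p_t)p_c(1−p_c)], with φ from 0 to 0.4. Probability of declaring non-inferiority (score test, one-sided 2.5%):

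| True test rate | Margin 10 | Margin 15 | Margin 20 |
|---|---|---|---|
| 90% | 34–43% | 62–79% | 86–96% |
| 85% | 10–12% | 28–38% | 55–72% |
| 80% | about 2% | 9–11% | 25–35% |

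**5. Smallest margin supportable at 80% power.** Same method, in points; each range runs from φ = 0 to φ = 0.4.

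| True rates (test / comparator) | 50 pairs | 40 evaluable pairs |
|---|---|---|
| 80 / 80 | 22.5–18.5 | 25.6–21.2 |
| 90 / 90 | 18.3–15.7 | 20.5–18.0 |
| 95 / 95 | 14.7–13.1 | 16.6–14.6 |
| 88 / 90 | 20.9–18.3 | 23.5–19.9 |
| 85 / 90 | 24.8–21.6 | 27.3–24.3 |

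The formula in step 2, solved for the margin with p from 0.85 to 0.95 and ρ from 0 to 0.5, gives about 8.6 to 20 points for 50 pairs. The method and the assumed ranges account for the difference.

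If the outcome is a score with roughly normal paired differences and no true difference (paired t, one-sided 2.5%), the supportable margin is 0.40 SD of the within-patient difference with 50 pairs and 0.45 SD with 40. A true deficit adds to this one for one.

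**6. Why a non-significant difference is no substitute.** Exact McNemar test (not named in the plan), 50 pairs, comparator at 90%, φ from 0 to 0.4:

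| True deficit | Probability of p ≥ 0.05 |
|---|---|
| 5 points | 94–93% |
| 10 points | 80–72% |
| 15 points | 59–40% |
| 20 points | 37–14% |

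**The case against.** The strongest reply is that Data Analyses is silent rather than wrong. A non-inferiority analysis is itself inference on a difference, so the sentence does not exclude a confidence-interval rule, and nothing says that p > 0.05 would be read as non-inferiority. That is correct, and step 6 shows only what such a reading would cost. Silence still leaves the aim without a margin, and an interval without a margin reaches no conclusion.

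The primary objective does fix a domain, a time point and instruments. This also stands: the gap is the missing single variable and the missing choice between FDI and USPHS.

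The rates, correlations, dichotomy and attrition are all assumed, and the supportable margin moves with them. That is so, but the defect does not depend on them; step 3 alone shows it.

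Only the aim uses the term non-inferiority, while the objectives and design speak of assessing and evaluating. An estimation aim would therefore fit most of the document, and it is a legitimate remedy. Finally, linking pain to discomfort is an inference, since the documents never connect them. That is a further reason to define the discomfort outcome.

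**Conclusion.** The concern holds and must be fixed while the non-inferiority aim stands. Margin, single endpoint and decision rule are all absent, so the plan does not determine its headline conclusion. This rests on the text alone.

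The size is illustrative. With a comparator at 90% and a test material truly at 85%, the chance of declaring non-inferiority runs from 10–12% at a 10-point margin to 55–72% at 20 points. These figures assume a success/failure outcome, 50 evaluable pairs and within-patient correlation of 0 to 0.4. A fuller unpublished plan cannot be ruled out, though none is mentioned.

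**What to change.** Replace the Data Analyses sentence with text that does the following:

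- **Endpoint.** Name one primary 36-month variable from FDI or USPHS, either binary (listing the acceptable grades) or score-based. State how lost or replaced restorations count. The other scale is supportive.
- **Decision rule.** Declare non-inferiority only if the lower limit of the two-sided 95% CI for the paired difference (Surefil one minus Venus Pearl, higher being better) lies above minus the margin. State that p > 0.05 on a difference test is not evidence of non-inferiority. For a binary outcome, a score-type paired interval is an option: its one-sided error is 1.9–2.4%, against 2.9–5.0% for Wald (90% comparator, 50 pairs, margins 10–20 points).
- **Margin.** Justify it on clinical grounds without reference to comparative results, and state whether anyone setting it has seen such results.
- **Feasibility.** State what 50 evaluable pairs support at 80% power on the sponsor's own assumed rates, correlation and attrition. Step 5 of the working indicates the order of magnitude. This shows feasibility and does not justify a margin.
- **Discomfort.** Name one pain measure and time point with its own margin and paired CI rule, and say how it combines with the primary (both required, or tested in sequence). Otherwise remove discomfort from the non-inferiority aim.
- **Fallback.** If no margin can be justified, or 50 pairs cannot support it, change the aim to estimating the paired difference with a 95% CI and drop the non-inferiority claim.

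The cost is wording only, with no extra patients or procedures, provided the sponsor accepts what 50 pairs support or drops the claim. Keeping the claim with a tighter margin could need more patients. The supportable margin may look wide: about 16–18 points if both rates are 90%, or 22–25 if the test rate is truly 85%.

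By Study timetable the start was anticipated for September 2022, so on schedule no 36-month data would exist before about September 2025. Early visits may already have taken place by the document date of 9 February 2024, so the pain measure named should be one actually being collected.

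### Does the analysis sentence commit this split-mouth trial to an unpaired comparison with wrong standard errors?

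*Combined protocol and SAP*

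**What the plan says.** The Data Analyses section gives the method in a single sentence: "The differences between the two groups will be analyzed using a descriptive and inferential statistical analysis". The only other sentence there names the university department that will do the work, which is also the principal investigator's department.

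The design is described in three other places. The title calls the trial split-mouth. The opening page has "Anticipated number of subjects: 50 (split-mouth design, i.e. Surefil one n=50, and Venus Pearl n=50", so the two counts of 50 appear inside a parenthesis that ties them to the split-mouth layout. The Study design section has "This is a split-mouth randomized clinical investigation conducted to evaluate clinical performances".

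Two further statements bear on the point. The aim, under Background and overall aim, is "The aim of this study will be to demonstrate non-inferiority in terms of clinical performance and patient discomfort". The inclusion criteria ask for "Patients who present at least 2 cervical lesions on canines and / or upper premolars on vital teeth"; with 50 patients and 50 restorations per material, this works out at one restoration of each material per patient.

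**The concern.** Two restorations in one mouth share a patient, with the same oral hygiene and the same person reporting pain. Their outcomes are likely to be correlated, and a two-sample chi-square, Mann-Whitney or unpaired t test assumes that they are not. The only analytic wording in the plan speaks of two groups, and the pairing is never mentioned beside it. A reader could conclude that the analysis will set 50 restorations against 50 as if they came from 100 people.

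If so, positive correlation would make the standard error too large and waste the precision that the split-mouth design provides. In a non-inferiority test this means lost power. In an ordinary test of difference it makes a non-significant result more likely, and such a result might be misread as success. Leaving the choice open also lets it be made after the data are seen.

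**Working it through.** **What the text commits to.** Set side by side, the analysis sentence gives a target (a difference between materials) and no method, while the title, sample-size line and Study design section give the pairing. The sentence contains no sample size; a reading of two independent groups of 50 arises only by joining it to the opening page, where the same counts are marked as split-mouth. McNemar's test, a paired risk difference and a signed-rank test all satisfy the sentence. So the text is silent on pairing, not in conflict with it.

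**The plan's own figure.** The 50 cannot be reproduced, because the documents give no alpha, power, margin, expected rate or correlation. As an indication, an unpaired non-inferiority calculation at 80% power gives from 19 to 252 per material over assumed success rates of 80% to 95% and margins of 10 to 20 points. The 50 is neither confirmed nor refuted.

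**Size of the effect if an unpaired method were chosen.** From the documents: n = 50 pairs. Assumed: success p = 0.90 on both materials, margin 15 points, one-sided alpha 2.5%, within-patient correlation ρ of 0, 0.2, 0.3 or 0.5.

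- Unpaired SE = √(2p(1−p)/n) = √(2 × 0.9 × 0.1/50) = 0.060, so the 95% half-width is 1.96 × 0.060 = 11.8 points.
- Paired SE = 0.060 × √(1−ρ).
- Ratio of unpaired to paired SE = 1/√(1−ρ).
- Actual one-sided error of the unpaired test = Φ(−1.96/√(1−ρ)).
- Power, paired = Φ(0.15/SE_paired − 1.96).
- Power, unpaired = Φ((0.15 − 1.96 × 0.060)/SE_paired), because the true spread is still the paired one.

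| ρ | Unpaired SE too large by | Half-width, paired (points) | Actual one-sided error, unpaired | Power, unpaired | Power, paired |
|---|---|---|---|---|---|
| 0 | 0% | 11.8 | 2.5% | 71% | 71% |
| 0.2 | 12% | 10.5 | 1.4% | 73% | 80% |
| 0.3 | 20% | 9.8 | 1.0% | 74% | 85% |
| 0.5 | 41% | 8.3 | 0.3% | 78% | 94% |

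For example, at ρ = 0.3 the paired SE is 0.060 × √0.7 = 0.0502. Paired power is Φ(0.15/0.0502 − 1.96) = Φ(1.03) = 85%. Unpaired power is Φ(0.0324/0.0502) = Φ(0.65) = 74%.

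With zero or positive correlation the unpaired error rate never exceeds 2.5%. Only negative correlation reverses this: at ρ = −0.2 the one-sided error would be 3.7%. Positive correlation is the usual expectation for two teeth in one mouth.

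**The case for a change.** The strongest case for acting is that an analyst could run unpaired tests and still comply with the plan, and that a sentence naming a within-patient method would cost almost nothing. The document is dated February 2024. With an anticipated start in September 2022, 36-month data could not arise before about September 2025, so the sentence could have been written before any primary outcome existed. The Data Analyses section shows no sign of redaction that would explain the silence.

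All of that is true, and the arithmetic behind the loss of power is sound. What stands is that the plan does not write down a paired method. It also does not say how it treats a pair with one restoration missing, or a patient with more than two eligible lesions. What does not stand is the step from there to a wrong analysis: permitting a poor choice is not prescribing it. The fear that a non-significant difference would pass as success depends on a test of difference being misread against a stated non-inferiority aim. The documents do not say that this will happen, and it concerns the missing margin and test, which is a separate question from pairing. Nor is pairing wholly free: intervals narrow only if the correlation is positive, and complete-pair methods drop pairs with one missing restoration.

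**Conclusion.** The concern does not hold as an error in the plan. The analysis sentence fits a paired analysis as well as an unpaired one, and the design is labelled split-mouth in every place that would guide the analyst. The missing method is a gap in detail that someone who knows the design fills sensibly, and a correct within-patient analysis needs no departure from the plan.

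The loss, if pairing were ignored, would be 0 to 16 points of power (94% − 78% at the top of the range) and a half-width of 11.8 points in place of 11.8 to 8.3. It would fall on the sponsor's chance of showing non-inferiority, not on the protection against a false claim. These sizes rest on an assumed 90% success rate, a 15-point margin and correlations from 0 to 0.5, none of which the documents give. The conclusion that the text does not prescribe an unpaired analysis needs none of these assumptions.
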